3 STATISTICAL METHODS

3.1 General Considerations

There are 3 planned analyses for this study: the primary analysis, the Season 2 analysis and the final analysis. The primary analysis will be conducted after all randomized subjects have completed follow-up through the first 5-month RSV season (ie, Season 1 Day 151 visit) and include all available Season 1 safety, efficacy, PK, and ADA data at the time of the data cutoff. The Season 2 analysis will be conducted after all CLD/CHD subjects have completed follow-up through the second 5-month RSV season (ie, Season 2 Day 151 visit) and include all available Season 1 data and Season 2 safety, efficacy, PK, and ADA data at the time of the data cutoff. The final analysis will be conducted when all subjects have completed the last visit of the study and include all data collected in the study.

At the time of the primary analysis, the Season 1 data will be unblinded to Sponsor/designated clinical research organization associated with the analysis, write-up and submission. To ensure the blinding of Season 2 treatment assignment for CHD/CLD subjects who were randomized to palivizumab arm in Season 1, any data with potential unblinding risk will be split by Season 1 and Season 2 by the corresponding third party data vendors and when the primary database lock (DBL) occurs, only unblinding data from Season 1 will be transferred to the Sponsor for analysis.

The site personnel, participants, and the study team members who participate in the advice or decisions involving study subjects and/or day-to-day interactions with the site, will remain blinded until the end of the study to ensure the trial integrity is maintained. Details of the unblinding process will be documented in a separated file of unblinding plan.

For the visit-based summaries for ADA, RSV neutralizing antibody, RSV serology, and clinical laboratory data, the summaries will be based on the scheduled days with adjusted analysis-defined visit windows. The adjusted analysis-defined windows will be based on the collection schedule listed in the protocol and summaries will be windowed to the closest scheduled visit for those data. Visit windows have been constructed so that every observation collected can be allocated to a particular visit. However, all data will be included in the listings. If multiple readings are recorded within a single analysis-defined visit window, the following rules will apply:

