3.6 Exploratory Analyses

3.6.1 Healthcare Resource Utilization (HRU)

For each season, the following summaries will be provided using the respective ITT population. The Season 1 summaries will also be repeated for each cohort (pre-term, CHD/CLD).

The magnitude of healthcare resource utilization (HRU; as measured by number of admissions to hospitals and duration of stay; number of admissions to the intensive care unit [ICU] and duration of stay; number requiring respiratory support and the duration of use; number requiring supplemental oxygen and the duration of use; number and type of visits to outpatient facilities [outpatient ED, urgent care, outpatient clinic] will be summarized by

treatment group and reported in 3 time periods: through 150 days post 1st dose (on ITT population), after 150 days post dose (on ITT population with Day 151 visit), and through 360 days post dose (on ITT population).

Specifically, the following summary tables by treatment group will be used to report the magnitudes of overall HRU for all medically attended LRTI (protocol defined, non-protocol defined, RSV, non-RSV):

- The number and percent of subjects who have had at least one of the following: hospitalization, ICU admission, requiring respiratory support, requiring supplemental oxygen, or visiting an outpatient facility (for any type of the outpatient facility). Similar summaries will also be provided by respiratory support subtype (CPAP or mechanical ventilation) and the type of outpatient facility. The percentage will be calculated based on ITT population for time interval through 150 days post 1st dose, on ITT population with Day 151 visit for time interval after 150 days post 1st dose, and on ITT population for time interval through 360 days post 1st dose.
- For each of the medical activities listed above, the total number of the activity for a subject who has had at least one respective event in the reporting time-period will be calculated and summarized by treatment group using descriptive statistics (mean, median, standard deviation [SD], minimum, and maximum).
- The total duration of each of the following (in days) will be calculated accumulatively throughout the reporting time-period and summarized by descriptive statistics (mean, median, SD, minimum, and maximum): hospital stay, ICU stay, use of respiratory support, or use of supplemental oxygen for the subjects who had at least one of the corresponding activities.

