Duration of each hospitalization will be calculated from the admission or deterioration date to discharge date. If the discharge date is missing because the subject died in the hospital, the duration of that hospital stay will be calculated from admission to the minimum of {Death Date, End-of-Study Date, Data Cutoff Date at the time of Primary Analysis}. Total duration of hospitalization is the cumulated days of each hospital stay throughout the reporting time-period.

Similarly, duration of each ICU admission, use of respiratory support, or use of supplemental oxygen will be calculated from start date to stop date or the end date, and the total duration of each medical intervention for a subject is calculated by summing the duration of all occurrences in the time interval of interest.

In addition to the overall HRU summary, the HRU for medically attended RSV LRTI (Protocol-defined) will be summarized through 150 days post 1st dose, after 150 days post 1st dose, and through 360 days post 1st dose. The same conventions used for the overall summary (eg, patient population included in a specific summary) will be applied for the respective

events and the HRU must occur during the event being summarized. Only the subjects with protocol-defined medically attended RSV LRTI will be included in the summary.

In addition, the number of pre-specified OTC medication (analgesics/antipyretics) use will be summarized by treatment group and overall through one week after dosing. The number of pre-specified prescription medication (systemic antibacterial agents) use; the number of anti-wheezing medication use, and the number of antiviral therapy use will be summarized by treatment group and overall through 150 days post 1st dose. The Anatomical Therapeutic Chemical (ATC) codes for these medications will be provided in a separated file provided by medical monitor prior to DBL for primary analysis.

The number and percentage of subjects with pre-specified prescription medications (systemic antibacterial agents) use through 150 days post dose will be provided. The number of use per subject (for those with the medication use) will be summarized through 150 days post dose using descriptive statistics (mean, median, SD, minimum, and maximum) by treatment group and for all subjects combined.

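### SAP 3.6.1 ends fatal hospital stays no later than the primary-analysis cutoff, so in the Season 2 and final analyses a stay ending after that date can be truncated or negative

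*SAP*

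**What the plan says.** SAP 3.6.1 gives the general rule first: "Duration of each hospitalization will be calculated from the admission or deterioration date to discharge date". It then adds an exception: "If the discharge date is missing because the subject died in the hospital", the stay runs from admission to the minimum of three dates: the date of death, the date of end of study, and "Data Cutoff Date at the time of Primary Analysis". The next paragraph handles ICU stay, respiratory support and supplemental oxygen in a similar manner, from a start date to a stop date or an end date. It does not say what that end date is.

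The section opens with its scope: "For each season, the following summaries will be provided using the respective ITT population". The reporting periods are through 150 days, after 150 days and through 360 days post dose.

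SAP 3.1 sets the timing: "There are 3 planned analyses for this study: the primary analysis, the Season 2 analysis and the final analysis". The primary analysis follows the Season 1 Day 151 visit of all randomized subjects. For the last of the three, "The final analysis will be conducted when all subjects have completed the last visit of the study and include all data collected in the study". SAP 2.2 follows the CLD/CHD cohort to one year after Season 2 Dose 1.

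**The concern.** The third date in the minimum is fixed at the first of three analyses, but the rule serves all of them. Data keep accruing after the primary cutoff: the rest of Season 1 follow-up for later-randomized infants, and much or all of Season 2 for the CLD/CHD cohort. For a fatal stay that ends in that later period, the primary cutoff is the earliest of the three dates, so it becomes the end of the stay although it precedes the death.

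At stake are the duration summaries (mean, median, SD, minimum, maximum). SAP 3.6.1 takes these only over infants who had the activity, so the denominators are small and one impossible value can show. No primary or secondary endpoint is touched.

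**Working it through.** The plan gives no figure on this point to reproduce. The check applies the rule as date arithmetic.

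**Inputs from the documents.** The three-date minimum (SAP 3.6.1); the three analyses and their timing (SAP 3.1); follow-up to one year after Season 2 Dose 1 (SAP 2.2); Season 1 Day 361 and Season 2 Day 1 may be the same visit (Protocol Table 5, footnote b).

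**Assumptions.** The timeline is that of the last-randomized CLD/CHD infant: Season 1 Day 1 = day 1, Season 2 Day 1 = day 361, end of study E = 361 + 360 = day 721. The true fatal stay is 10 days, with no discharge date entered. The documents do not give the primary cutoff C, so it is varied over days 151, 181 and 241.

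**Formula.** Duration = min(D, E, C) - A, where A is admission and D is death.

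| Fatal 10-day stay | C = 151 | C = 181 | C = 241 |
|---|---|---|---|
| Ends before the cutoff (A = C - 20, D = C - 10) | 10 | 10 | 10 |
| Straddles the cutoff (A = C - 4, D = C + 6) | 4 | 4 | 4 |
| Season 1, admitted 30 days after the cutoff | -30 | -30 | -30 |
| Admitted Season 2 Day 1 (A = 361) | -210 | -180 | -120 |
| Admitted Season 2 Day 151 (A = 511) | -360 | -330 | -270 |
| Admitted Season 2 Day 350 (A = 710) | -559 | -529 | -469 |

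For example, Season 2 Day 1 with C = 151 gives min(371, 721, 151) - 361 = -210. If C is replaced by the cutoff of the analysis that reports the completed stay, every row returns 10.

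**Where the rule can bite.** In the primary analysis the third term is essentially inert: a death in the data by then lies on or before the cutoff, so the minimum is already the death date or an earlier end-of-study date. In the later analyses, Season 1 stays in the through-150-days period begin before the cutoff, because every infant has reached Day 151 by then. They can be truncated but not negative. Negative values are confined to the later Season 1 periods and Season 2.

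**Effect on a mean over n hospitalized infants.** Assume one 10-day fatal stay starting 200 days after the cutoff, counted as -200. The shift is (10 - (-200))/n = 210/n:
- n = 5: 42 days
- n = 10: 21 days
- n = 20: 10.5 days

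For the straddling stay in the table the shift is (10 - 4)/n = 6/n: 1.2, 0.6 and 0.3 days.

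**Is a small n plausible?** The RSV hospitalization rate quoted in SAP 2.4 is 1.9%, from palivizumab recipients in a prior study. Applied for illustration to the planned Season 2 arms, it gives 200 x 0.019 = 3.8 infants and 50 x 0.019 = 0.95 in each of the other two. The overall table covers all medically attended LRTI, so its n is larger and the shift smaller.

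**The case against.** The strongest reply is that the phrase was written with the primary-analysis run in mind and that a programmer would substitute the right cutoff later. That may be the intent, but the SAP does not say so, and the term does essentially no work in the primary analysis. If it is simply ignored afterwards, the later analyses have no stated cutoff.

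The second reply is that the conditions rarely coincide. The stay must belong to a medically attended LRTI (SAP 3.6.1; Protocol 4.3.6), the infant must die in hospital, the discharge date must be missing for that reason, and the stay must end after the primary cutoff. If the site enters the death date as the discharge date, the rule never applies. Infants randomized early may also have Season 2 stays that end before the cutoff, and these are unaffected. All of this stands. The only death figure in the documents is 5 among 1,447 dosed in the Phase 2b study (about 0.35%, all causes; Protocol 1.4.1). Those were healthy preterm infants, so the rate does not carry over to this higher-risk population, but it gives no ground for expecting several cases.

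Third, a negative stay would be visible in a listing or in the reported minimum. This largely stands for an infant with one stay. Truncation of a straddling stay is less conspicuous, though its effect is much smaller. Because SAP 3.6.1 adds up an infant's stays, a negative one could also be partly hidden by an earlier valid one.

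**Conclusion.** The rule is wrong as written for the two later analyses, but the consequence is minor and conditional. A qualifying fatal stay that ends after the primary cutoff is truncated, or negative if admission is also later. There may be no such stay. The shifts of 42, 21 and 10.5 days rest on assumed inputs (one 10-day stay, a 200-day gap, and 5, 10 or 20 hospitalized infants) and are not predictions.

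Three stronger readings are tempting, and the documents do not support them:
- That both later analyses will report wrong durations. They will not if no stay meets all the conditions.
- That ICU, respiratory-support and oxygen durations carry the same error. SAP 3.6.1 does not repeat the three-date minimum for them. It leaves their end date undefined, which is an ambiguity.
- That the trial's conclusions are affected. HRU is exploratory (Protocol 2.1.2), and SAP 1 states that there is no formal hypothesis testing for safety or efficacy.

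**What to change.** In SAP 3.6.1, replace the third date in the minimum with the data cutoff date of the analysis being performed. In the following paragraph, define the end date for ICU stay, respiratory support and supplemental oxygen in the same way. The cost is one phrase and one short definition. Data collection, sample size and all other endpoints are unchanged, and fatal stays that ended before the primary cutoff keep the same duration.

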3.6.2 Caregiver Burden

For each season, the following summaries will be provided using the respective ITT population. The Season 1 summaries will also be repeated for each cohort (pre-term, CHD/CLD).

Caregiver burden (measured by days of work the caregiver missed, days of daycare/babysitting the subject missed) will be summarized for subjects with medically attended RSV LRTI (Protocol-defined) by treatment group for subjects who have had at least an event in the time-period of reporting. These summaries will be presented through 150 days post 1st dose, after 150 days post 1st dose, and through 360 days post 1st dose using similar reporting convention as described previously.

For each of the events mentioned above and each time-period of reporting, the accumulated total days of work the caregiver missed and the accumulated total days of daycare/babysitting the subject missed will be calculated for each subject and presented using descriptive statistics (mean, median, SD, minimum, and maximum) by treatment group. For each treatment group, the average caregiver burden (ie, the average number of days of work the caregiver missed, the average number of days of daycare/babysitting the subject missed) for a respective event will be calculated as the total caregiver burden across subjects who have had at least one of the events divided by the total number of the events among these subjects in the time interval of interest. Similar summary will also be provided by the status of hospitalization (at least one or none) that is caused by a respective event mentioned above.

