2.1.2 Exploratory Objectives and Associated Endpoints

Table 3 Exploratory Objectives and Endpoints

Type	Objective	Endpoint
RSV neutralizing antibody	To determine anti-RSV neutralizing antibody levels in serum afforded by a single dose of MEDI8897 compared to 5 monthly doses of palivizumab	
 Anti-RSV neutralizing antibody levels (IU/mL) in serum for MEDI8897 recipients compared to palivizumab recipients Summary of serum RSV neutralizing antibody levels (may include GMT, GMFR, C_{max}, apparent clearance, and $t_{1/2}$)
RSV serology	To evaluate exposure to RSV by measuring seroresponses to different RSV proteins in MEDI8897 and palivizumab recipients	
 Antibody levels to RSV F, Ga, Gb, or N at different time points Changes in RSV antibody levels (seroresponse) indicating exposure to RSV
	To evaluate the levels of maternal RSV-specific antibody in MEDI8897 and palivizumab recipients	
 RSV antigen antibody levels (AbU/mL) to multiple RSV antigens Summary of serum RSV antibody levels (may include GMT, GMFR, seroconversion rates, apparent clearance, and $t_{1/2}$)
HRU and caregiver burden	To assess HRU and caregiver burden for MEDI8897 recipients compared to palivizumab recipients	
 Magnitude of HRU (eg, number of admissions to hospitals and ICUs and duration of stay; number of subjects who require respiratory support and supplemental oxygen and the duration of use; number and type of outpatient visits [eg, ER, urgent care, outpatient clinic]; and number of prescription and OTC medications and duration of use) for MEDI8897 recipients compared to palivizumab recipients Caregiver burden (eg, caregiver missed work days, subject absence from day care) for subjects with medically attended LRTI caused by RT-PCR-confirmed RSV

Table 3 Exploratory Objectives and Endpoints

Type	Objective	Endpoint
RSV resistance monitoring	To characterize resistance to MEDI8897 and palivizumab through genotypic and phenotypic analyses	Genotypic analysis and susceptibility of RSV variants to neutralization by MEDI8897 and palivizumab
RSV LRTI after Day 151	To assess the incidence of medically attended LRTI due to RT-PCR-confirmed RSV, compared to palivizumab after Day 151	Incidence of medically attended LRTI (inpatient and outpatient) due to RT-PCR-confirmed RSV from Day 152 to Day 361 for Season 1 and Season 2

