4.3.6 Healthcare Resource Utilization and Caregiver Burden

Information on HRU and caregiver burden will be collected for all events of medically attended LRTI (see [Table 5](#) and [Table 6](#)). This will include admission to and duration of hospital and intensive care unit (ICU) stay, number of subjects who require respiratory support and supplemental oxygen use, duration of respiratory support and supplemental oxygen use, number and type of outpatient visits (eg, ER, urgent care, outpatient clinic), and the number of prescription and over-the-counter (OTC) medications and their duration of use. Caregiver burden will be assessed through, for example, caregiver missed work days and the subject's absence from day care.

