4.8.6.3 Healthcare Resource Utilization and Caregiver Burden

The magnitude of HRU (eg, number of admissions to hospitals and ICUs and duration of stay; number of subjects who require respiratory support and supplemental oxygen and the duration of use; number and types of outpatient visits, eg, ER, urgent care, outpatient clinic; and number of prescription and OTC medications and duration of use) will be summarized overall by treatment group and for subjects with at least one medically attended LRTI (protocol defined) caused by RT-PCR-confirmed RSV.

Caregiver burden (eg, caregiver missed work days, subject absence from day care) for subjects with medically attended LRTI (protocol defined) caused by RT-PCR-confirmed RSV will be summarized by treatment group.

The HRU and caregiver burden summaries will be performed on the ITT Population.

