2.1.3 Exploratory Study Objectives

- 4 To assess HRU and caregiver burden for MEDI8897 recipients compared to palivizumab recipients
- To determine anti-RSV neutralizing antibody levels in serum afforded by a single dose of MEDI8897 compared to 5 monthly doses of palivizumab
- To evaluate exposure to RSV by measuring seroresponses to different RSV proteins in MEDI8897 and palivizumab recipients and to evaluate the levels of maternal RSV-specific antibody in MEDI8897 and palivizumab recipients

- 7 To characterize resistance to MEDI8897 through genotypic and phenotypic analyses
- 8 To assess the incidence of medically attended LRTI due to RT-PCR-confirmed RSV, compared to palivizumab after Day 151 (between Day 152 and Day 361)

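### HRU counts and durations and caregiver-burden averages are taken only over infants with an event, so they describe severity given an event; no caregiver-burden figure on the ITT denominator is planned

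*SAP*

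**What the plan says.** The objective, in SAP 2.1.3 and in the protocol's table of exploratory objectives, is "To assess HRU and caregiver burden for MEDI8897 recipients compared to palivizumab recipients". The caregiver endpoint attached to it in Protocol 2.1.2 is narrower: "Caregiver burden (eg, caregiver missed work days, subject absence from day care) for subjects with medically attended LRTI caused by RT-PCR-confirmed RSV". Protocol 4.8.6.3 keeps that restriction for caregiver burden, says that HRU "will be summarized overall by treatment group and for subjects with at least one medically attended LRTI (protocol defined) caused by RT-PCR-confirmed RSV", and closes with "The HRU and caregiver burden summaries will be performed on the ITT Population".

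SAP 3.6.1 and 3.6.2 both begin from the ITT population of each season. The denominators then differ by table:

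- **HRU, any use:** number and percentage of infants with each activity, on ITT (ITT with a Day 151 visit for the period after 150 days).
- **HRU, counts:** only infants with at least one such activity.
- **HRU, durations:** hospital stay, ICU stay, "use of respiratory support, or use of supplemental oxygen for the subjects who had at least one of the corresponding activities".
- **HRU for RSV LRTI:** "Only the subjects with protocol-defined medically attended RSV LRTI will be included in the summary".
- **Caregiver burden:** "by treatment group for subjects who have had at least an event in the time-period of reporting", plus an average whose divisor is the number of events, plus the same summary by hospitalisation status.

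No total or mean per randomised infant is specified for counts or days.

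**The concern.** Both antibodies are given to prevent the event that decides who enters these tables. Infants with an RSV LRTI are a subset chosen after randomisation, on the outcome, so the two subsets are not protected by randomisation. A mean within them answers how heavy an event is once it occurs. The objective asks how much use and burden recipients of each drug have.

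Two things can follow. If an arm prevents events evenly across severities, its conditional mean does not move and the benefit is absent from that table. If it prevents mainly mild cases, its remaining cases are heavier on average and its conditional mean rises while its total burden falls. SAP 3.5.1.2 and 3.7 warn about selective Season 1 dropout when Season 2 arms are compared. Sections 3.6.1 and 3.6.2 carry no similar caution about selection on the event.

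**Working it through.** **Inputs from the documents** (Protocol 4.8.2, SAP 2.4): 300 palivizumab and 600 MEDI8897 infants in Season 1; an assumed 6% RSV LRTI rate in each arm; a split of 1.9% hospitalised and 3.9% outpatient. Protocol 4.3.6 states: "Information on HRU and caregiver burden will be collected for all events of medically attended LRTI". An infant followed without such an event therefore adds zero LRTI-related days.

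**Assumed inputs:** days lost per event, which the documents do not give; one event per affected infant; any event rate other than 6%.

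**1. The plan's own figure.** 300 × 0.06 = 18 and 600 × 0.06 = 36, as stated. The unrounded split, 1.9 + 3.9 = 5.8%, gives 17.4 and 34.8. The event-only tables therefore leave out about 94% of each arm (282 of 300; 564 of 600).

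**2. Formula.** Days per 100 randomised = 100 × (infants with an event × mean days per affected infant) ÷ N.

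**3. Events halved evenly.** Palivizumab 6%, MEDI8897 3%, so 18 events in each arm.

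| Assumed days per event | Conditional mean, palivizumab / MEDI8897 | Days per 100 randomised, palivizumab / MEDI8897 |
|---|---|---|
| 2 | 2 / 2 | 12 / 6 |
| 5 | 5 / 5 | 30 / 15 |
| 10 | 10 / 10 | 60 / 30 |

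For the middle row: 100 × 18 × 5 ÷ 300 = 30 and 100 × 18 × 5 ÷ 600 = 15. At 6% in both arms the figures are 30 and 30, and the conditional mean loses nothing in the comparison.

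**4. Only outpatient cases halved on MEDI8897** (1.9% hospitalised and 3.9 ÷ 2 = 1.95% outpatient, total 3.85%), with 7 days if hospitalised and 2 if not:

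- Palivizumab: 1.9 × 7 + 3.9 × 2 = 21.1 days per 100; conditional mean 21.1 ÷ 5.8 = 3.64.
- MEDI8897: 1.9 × 7 + 1.95 × 2 = 17.2 days per 100; conditional mean 17.2 ÷ 3.85 = 4.47.

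The arm with less total burden has the higher conditional mean. With 5 and 1 days the conditional means are 2.31 and 2.97, against 13.4 and 11.45 per 100. With 10 and 3 days they are 5.29 and 6.45, against 30.7 and 24.85.

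**5. The same example split by hospitalisation status**, as SAP 3.6.2 also plans: 7 and 7 days if hospitalised, 2 and 2 if not. The reversal disappears. The means are then equal and still do not show the prevented cases.

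**The case against.** Several points on the other side stand.

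- A reader might infer that prevention gets no credit anywhere. It does for HRU: the percentage of ITT infants with each activity is planned, and it falls when events are prevented. RSV LRTI incidence is also reported on ITT with exact 95% intervals and by care setting (SAP 3.5.1.1).
- A reader might infer that the SAP breaks the protocol's ITT rule. For caregiver burden it does not. Protocol 2.1.2 and 4.8.6.3 limit that endpoint to infants with RSV LRTI, and SAP 3.6.2 carries this out. The mismatch is between the protocol's objective and its endpoint.
- A reader might infer that the tables will mislead on direction. That needs a different mix of mild and severe cases between arms, and the planned hospitalisation split removes the reversal in the example above. The plan expects numerically similar efficacy, and at equal rates and severity mix the conditional comparison is undistorted.
- Point estimates can be recovered as conditional mean × number affected ÷ N, provided burden is recorded for every affected infant. What cannot be recovered is an interval.
- Zero is not a known value for everyone in ITT. Under Protocol 4.1.5 and 4.1.6, withdrawn infants give no further data and undosed infants are not followed.
- The study is descriptive, and even the primary efficacy endpoint gets only per-arm intervals. A between-arm interval for an exploratory endpoint would ask for more.

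None of this puts a caregiver-burden figure on the randomised denominator into the plan.

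**Conclusion.** The point holds in a limited form. HRU counts and durations and every caregiver-burden average are conditional on a post-randomisation event; they describe severity and are not comparisons of randomised groups. HRU has a partial remedy in the ITT percentages. Caregiver burden has none, so the stated comparison of recipients is not answered directly.

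The size depends on assumptions outside the documents. It is nil in the between-arm comparison at equal rates and severity mix. With a halved event rate, a twofold difference in burden per randomised infant appears as equal conditional means, whatever days per event are assumed. The documents do not support the broader readings that prevention is ignored throughout, that the SAP departs from the protocol's caregiver endpoint, or that the planned tables must point the wrong way. This is a cheap improvement to exploratory outputs; no primary or secondary conclusion changes.

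**What to change.** In SAP 3.6.1 and 3.6.2, add by arm and reporting period, per 100 randomised infants:

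- total counts and total days of LRTI-related HRU;
- total missed work days and missed daycare days due to protocol-defined RSV LRTI.

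Use the ITT denominator, and ITT with a Day 151 visit for the period after 150 days, as the HRU percentages already do. Base the totals on observed events, as in SAP 3.5, counting zero for infants with no recorded event. State that infants who withdrew or were not followed contribute observed data only, or give the rate per infant-time followed as a check. Give a per-arm 95% bootstrap interval; a between-arm difference is optional. Note in SAP 3.6.2 that the caregiver total supplements the protocol endpoint.

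Keep the per-affected-infant and per-event tables, labelled as conditional on an event and not for between-arm comparison.

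The cost is SAP wording and a few extra tables from data already collected. The values will be skewed and mostly zero, so the intervals will be wide, more so if RSV circulation is low.
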